4.2 Inclusion criteria

In order to be eligible for this study, a case must meet all of the following criteria:

- Age (at primary gastrointestinal cancer diagnosis) <25 years
- Diagnosis of a primary gastrointestinal malignancy as an individual's first primary malignancy, based on:
 - Primary site "digestive organs" (ICD-O-3 topography codes C015-C026)
 - Behavior code "malignant" (ICD-O-3 behavior code 3)

Selection of only those cases with a primary gastrointestinal malignancy as their first primary malignancy is done by setting the Multiple Primary Selection option on the Selection tab of SEER*Stat software to First Malignant Primary Only (Non-reported Assumed Malignant).

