Subtype	Primary site classification subgroups	Additional staging scheme subgroups	Grading scheme subgroups	Histologic classification subgroups	Surgery primary site (RX Summ--Surg Prim Site (1998+) variable)	Total hepatectomy with transplant (RX Summ--Surg Prim Site (1998+) variable)	Radiation (Radiation recode variable)	Chemotherapy (Chemotherapy recode (yes, no/unk) variable)
BL	ICD-O-3 C015-C026	Ann Arbor stage I-IV	NR	NR	Yes (values 10-90); No or unknown (values 0 and 99)	NR	Yes (all subtypes); No or unknown (incl. "refused" and "recommended, unknown if administered")	Yes; No or unknown
UESL	NR	N/A	NR	NR	Yes (values 10-90); No or unknown (values 0 and 99)	Yes (values 61 and 75); No or unknown (other values)	Yes (all subtypes); No or unknown (incl. "refused" and "recommended, unknown if administered")	Yes; No or unknown
NEN	ICD-O-3 C015-C017, C018.1 (appendix), C018 excl. C018.1, C019-C026	AJCC stage I-IV	ICD-O-3 Grade I-III	Rare Cancer Classification Cat. 1: 230-231 (well differentiated) vs. Cat. 2: 232-233 (poorly differentiated & MiNEN)	Yes (values 10-90); No or unknown (values 0 and 99)	NR	Yes (all subtypes); No or unknown (incl. "refused" and "recommended, unknown if administered")	Yes; No or unknown
HB	NR	N/A	ICD-O-3 Grade I-IV	NR	Yes (values 10-90); No or unknown (values 0 and 99)	Yes (values 61 and 75); No or unknown (other values)	Yes (all subtypes); No or unknown (incl. "refused" and "recommended, unknown if administered")	Yes; No or unknown
HCC	NR	AJCC stage I-IV	ICD-O-3 Grade I-IV	Rare Cancer Classification Cat. 1: 52 (HCC, NOS) vs. Cat. 2: 53 (HCC, fibrolamellar)	Yes (values 10-90); No or unknown (values 0 and 99)	Yes (values 61 and 75); No or unknown (other values)	Yes (all subtypes); No or unknown (incl. "refused" and "recommended, unknown if administered")	Yes; No or unknown
GC	ICD-O-3 C016.0-C016.9	AJCC stage I-IV	ICD-O-3 Grade I-IV	ICD-O-3 Cat. 1: 8140 (AC, NOS), Cat. 2: 8210 + 8220 + 8221 + 8261 + 8263 (AC in polyp/adenoma), Cat. 3: 8480-8482 (MAC), Cat. 4: 8490 (SRCC), Cat. 5: remaining cases (others/unknown) ¹⁶	Yes (values 10-90); No or unknown (values 0 and 99)	NR	Yes (all subtypes); No or unknown (incl. "refused" and "recommended, unknown if administered")	Yes; No or unknown

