10.1 Primary study parameter(s)

Data is presented quantitatively (numerically). Continuous variables are summarized with medians and ranges, and categorical variables are summarized with frequencies and proportions. Age at diagnosis can also be summarized with frequencies and proportions, using 1-year age categories. Overall survival (OS) is estimated by the Kaplan-Meier method. OS is defined as the time from the date of

diagnosis until the date of death from any cause (event) or until the date of last follow-up. Survival curves may be compared with the log-rank test. Median follow-up is estimated using the reverse Kaplan-Meier method³².

The following descriptive statistics are minimally obtained:

Frequencies and proportions of the different gastrointestinal malignancies – specified in Table 2 – by age group (<18; 18-24 years at diagnosis) and by 1-year age categories (0-24 years). Age distributions of patients diagnosed with common gastrointestinal malignancies (BL, UESL, NEN, HCC, HB, GC, and CRC).

Stratified by age group (<18; 18-24 years at diagnosis):

Frequencies and proportions of the different gastrointestinal malignancies by primary anatomic site (ICD-O-3 topography codes C015-C026). Summarized sex and race and origin data of patients diagnosed with common gastrointestinal malignancies. Frequencies and proportions of surgery, radiation, and chemotherapy as part of the first course of treatment of patients with common gastrointestinal malignancies. Frequencies and proportions of different stages at diagnosis, different grades, and different histologic subtypes of patients diagnosed with CRC. Frequencies and proportions of CRC cases by primary anatomic site (ICD-O-3 topography codes C018.0-C018.9, C019.9, and C020.9). Kaplan-Meier curves depicting OS of patients diagnosed with common gastrointestinal malignancies. Estimated 1- and 5-year OS (with 95% confidence intervals) of patients diagnosed with common gastrointestinal malignancies. Kaplan-Meier curves depicting OS of CRC patients by i) stage at diagnosis, ii) by grade, and iii) by histologic subtype. Frequencies and proportions of patients with multiple primary cancers registered in 2000-2019 by common cancer subgroup (Table 3). Median total number of in situ/malignant tumors of patients diagnosed with common gastrointestinal malignancies.

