10.2 Secondary study parameter(s)

Data will be presented quantitatively (numerically); stratified by age group (<18; 18-24 years at diagnosis).

Age-adjusted incidence and mortality rates are calculated as the average annual number of cases or deaths per million person-years at risk, respectively. For mortality rates, calendar year and age (<18; 18-24 years) represent year and age at death, respectively. Incidence rates of the common gastrointestinal malignancies are based on SEER 17 incidence data (2000-2019); mortality rates of malignant neoplasms of the digestive organs (ICD-O-3 topography codes C015-C026) are based on mortality data of the total U.S. population (1969-2019). In addition, incidence-based mortality (IBM) rates – for cases registered in SEER 17 – may be calculated to partition mortality by digestive cancer subtype (BL, UESL, NEN, HCC, HB, GC, and CRC)³³. The annual population size is obtained from the Census Bureau. Rates are age-standardized using the age structure of the 2000 U.S. standard population. Rates are calculated using SEER*Stat software and plotted using 3-year moving averages³⁴. When 3-year moving averages vary greatly, rates may be plotted using 5- or 7-year moving averages. Trends over time in incidence and mortality are analyzed by Poisson regression, with the calendar year as a continuous regressor variable. In addition, trends over time may be evaluated by linear regression modelling – a method frequently used in prior studies^{34,35} – to allow easier comparisons between studies, as well as with Jointpoint regression modelling to identify change points in the trends. Results are reported as average annual percent changes (AAPC) along with 95% confidence intervals and *P* values.

Trends over time in stage at diagnosis or first course treatments of patients with common GI malignancies are tested with logistic regression, with year of diagnosis as a continuous variable³⁴. The proportions of each stage at diagnosis or treatment category are plotted as weighted 3-year moving averages in percentages. When weighted 3-year moving averages vary greatly, results may be plotted using weighted 5- or 7-year moving averages.

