Trends over time in OS of patients with common GI malignancies are evaluated by Cox regression analysis, with year of diagnosis as a continuous variable. The estimated 1- and 5-year OS of patients with common GI malignancies are plotted as percentages by diagnostic time period. For the diagnostic period 2015-2019, 5-year OS is not available due to insufficient follow-up. In addition, changes over

time in OS of patients diagnosed with common GI malignancies may be visualized by plotting separate Kaplan-Meier curves for each diagnostic time period¹⁶.

To explore independent prognostic factors for overall survival of patients with common GI malignancies, multivariable Cox regression analysis is performed with age at diagnosis, sex, race and origin, year of diagnosis, stage at diagnosis, and histologic category (when relevant; see Table 3) as included variables.

Table 4. Multivariable Cox regression analysis

	BL			UESL			NEN			HB			HCC			GC			CRC		
	No. at risk	HR (95% CI)	P	No. at risk	HR (95% CI)	P	No. at risk	HR (95% CI)	P	No. at risk	HR (95% CI)	P	No. at risk	HR (95% CI)	P	No. at risk	HR (95% CI)	P	No. at risk	HR (95% CI)	P
Age at diagnosis																					
Sex																					
Male		Reference			Reference			Reference			Reference			Reference			Reference			Reference	
Female																					
Race & origin																					
NH-White		Reference			Reference			Reference			Reference			Reference			Reference			Reference	
NH-Black																					
NH-Other/Unknown																					
Hispanic																					
Year of diagnosis																					
Stage																					
Localized																					
Regional		Reference			Reference			Reference			Reference			Reference			Reference			Reference	
Distant																					
Unknown/unstaged																					
Histology																					
Category 1		NR			NR						NR										
Category 2								Reference						Reference						Reference	
Category 3																					
Category 4																					
Category 5																					

NH, non-Hispanic; NR, not relevant

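### Table 3 sets appendiceal neuroendocrine neoplasms (NEN) apart, but no planned NEN survival or prognostic analysis uses the split, so a change in site mix could pass for a survival trend

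*Combined protocol and SAP*

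**What the plan says.** Table 3 (Section 8) gives the NEN primary-site subgroups as "ICD-O-3 C015-C017, C018.1 (appendix), C018 excl. C018.1, C019-C026", so appendix is its own subgroup. The NEN histologic categories in the same row go by differentiation, not site: "Rare Cancer Classification Cat. 1: 230-231 (well differentiated) vs. Cat. 2: 232-233 (poorly differentiated & MiNEN".

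The outcome analyses do not take up the site split:

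- **Descriptive survival (Section 10.1).** The planned output is "Kaplan-Meier curves depicting OS of patients diagnosed with common gastrointestinal malignancies", with 1- and 5-year OS, by cancer and age group. For CRC, further curves by stage, grade and histology are listed. For NEN, none by site is listed.
- **OS trend (Section 10.2).** "Trends over time in OS of patients with common GI malignancies are evaluated by Cox regression analysis, with year of diagnosis as a continuous variable". No other covariate is named.
- **Prognostic model (Section 10.2).** "multivariable Cox regression analysis is performed with age at diagnosis, sex, race and origin, year of diagnosis, stage at diagnosis, and histologic category". Table 4 has no row for site.
- **Incidence trend (Section 10.2).** "Trends over time in incidence and mortality are analyzed by Poisson regression, with the calendar year as a continuous regressor variable", with each common cancer as the unit.

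Site appears in Section 10.1 as a frequency table over C015-C026, by age group and not by calendar period. At that three-character level the appendix lies inside C018. The item Primary Site - labeled is already in the Table 1 retrieval list.

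**The concern.** Secondary objective 1 asks whether OS has changed over time, and objective 2 looks for independent prognostic factors. A group that combines sites with different survival has a pooled survival that depends on the mix. If the mix drifts with calendar year, a model containing only year assigns the drift to year. A reader of the NEN result could then conclude that NEN survival improved or worsened when it stayed the same at every site. Because site is not tabulated by period, the specified output would not show whether this had happened.

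The prognostic model is exposed to a lesser degree. If site carries information on survival beyond stage and differentiation, and is related to age or year, their hazard ratios may be partly site effects.

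**Working it through.** **Inputs.** The documents state no NEN count, number of deaths, appendix share or site-specific survival, so there is no planned figure to reproduce. Every survival and share value below is an assumption for illustration. The 20 diagnosis years 2000-2019, hence 19 yearly steps, come from the protocol.

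**1. Pooled survival when nothing changes within site.** Let p be the appendix share, with 5-year OS held at 99% (appendix) and 85% (other).

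Pooled OS = p × 0.99 + (1 − p) × 0.85

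- p = 0.40: 0.396 + 0.510 = 0.906
- p = 0.60: 0.594 + 0.340 = 0.934
- p = 0.75: 0.7425 + 0.2125 = 0.955

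Crude HR, late versus early = ln(OS late) / ln(OS early); per year = HR^(1/19).

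- 40% to 60%: ln 0.934 / ln 0.906 = 0.69, or 0.98 per year
- 40% to 75%: ln 0.955 / ln 0.906 = 0.47, or 0.96 per year
- With 90% instead of 85% for other sites: 0.71 and 0.50

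**2. Range over the survival gap.** The rise in pooled OS is the change in share times the gap in OS. For a share moving from 50% to 75%, with appendix at 99%:

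| Other-site 5-year OS | Rise in pooled OS |
|---|---|
| 99% | 0.25 × 0 = 0 points |
| 95% | 0.25 × 4 = 1.0 |
| 90% | 0.25 × 9 = 2.25 |
| 80% | 0.25 × 19 = 4.75 |
| 70% | 0.25 × 29 = 7.25 |

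Equal survival, or a stable share, gives zero.

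**3. What the 5-year OS plot can show.** Section 10.2 says 5-year OS is unavailable for 2015-2019. Assume a linear share change from 40% to 60% and 5-year periods. The mean share is 40 + 20 × 2/19 = 42.1% in 2000-2004 and 40 + 20 × 12/19 = 52.6% in 2010-2014. Pooled OS (0.85 + 0.14p) is then 90.9% and 92.4%, a spurious rise of 1.5 points rather than the full 2.8. The year-of-diagnosis Cox model and the 1-year OS plot span all years.

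**4. Does stage adjustment remove it?** Simulated Cox models, with no calendar trend within site: 600 patients, 200 runs, two-sided 0.05, stage HR 4, advanced stage in 10% of appendiceal and 40% of other cases, 5-year OS 99% versus 80%. Histology was not modelled.

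| Appendix share | Model | Median HR per year | Runs with P < 0.05 |
|---|---|---|---|
| 50% to 75% | year only | 0.968 | 23% |
| | + stage | 0.976 | 14.5% |
| | + stage + site | 1.000 | 4.5% |
| 30% to 75% | year only | 0.955 | 52.5% |
| | + stage | 0.970 | 21% |
| | + stage + site | 1.000 | 3.5% |

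At a constant 50% share, the year-only model gave an HR of 0.997 and P < 0.05 in 5% of runs. Stage removes part of the artefact and the site term removes it all.

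**5. Incidence.** With a constant total rate and a share moving from 50% to 75%, the fitted annual change in the pooled rate is 0.00%. If only appendiceal incidence grows, by 3%, 5% or 10% a year from a 50% share, the pooled change is 1.7%, 3.1% or 7.1%. That is a real rise in NEN incidence, but the pooled figure does not say where it arose.

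**The case against.** The case against has several good parts.

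- **Unknown premises.** Neither the survival gap nor a share shift is in the documents. A reader might infer from the malignant-behaviour requirement ("ICD-O-3 behavior code 3") that entry of appendiceal tumours drifted with coding practice. The protocol says nothing about coding over time, nor about the prognosis of appendiceal NEN. This stands: the point is conditional.
- **Existing adjustment.** The multivariable model already contains stage and well versus poorly differentiated histology. If appendiceal tumours do better because they are early and well differentiated, much of that is captured. This stands: the crude HRs in steps 1 and 2 do not apply to that model. The OS-trend model names no such adjustment.
- **Incidence.** A reader might infer that a share shift also creates an incidence trend. Step 5 shows that it does not.
- **Descriptive aim.** A reader might call the pooled OS meaningless. It validly describes all included NEN patients, the Section 10.1 list is a minimum, and the prognostic analysis is exploratory. This stands for the pooled estimate, but a permitted analysis is not a planned one, and the OS trend is a stated objective.
- **Sparse deaths.** At 99% 5-year OS, an assumed 300 appendiceal patients yield about 300 × 0.01 = 3 deaths by five years, before the split by age group. The NEN column of Table 4 already needs 10 coefficients (age 1, sex 1, race and origin 3, year 1, stage 3, histology 1). This stands and limits the remedy.

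**Conclusion.** The omission is plain from the text: an appendix subgroup is defined for NEN, and no specified survival or prognostic analysis uses it. The consequence is clearest for the OS-trend model and the OS plots by diagnostic period, where a changing site mix would appear as a trend. Its size rests on assumptions: a crude HR of about 0.69 over 19 years for a 40% to 60% shift at 99% versus 85%, 0.47 for 40% to 75%, and none if survival is equal or the share is stable.

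The documents do not support saying that the NEN results are confounded, only that they may be and that the planned output could not tell. In the multivariable model any confounding is residual. Pooled incidence trends are unbiased but cannot be attributed to a site. This is a cheap improvement to the plan, not a flaw that invalidates it.

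**What to change.** For NEN only, add to Sections 10.1 and 10.2 and to Table 4:

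1. Tabulate the appendix (C018.1) share by diagnostic period.
2. Report the incidence rate and average annual percent change, Kaplan-Meier curves, and 1- and 5-year OS for appendix and for all other sites, beside the pooled figures.
3. Include appendix versus other in the OS-trend and multivariable Cox models, as a covariate where events allow, and otherwise as a stratified baseline hazard, which uses no coefficient.
4. Fit a separate appendiceal OS trend only if deaths suffice.
5. Interpret any NEN survival trend from the site-adjusted results.

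The cost is a few lines of SAP wording, using data already retrieved. The downside is wider intervals within site, one more coefficient where the covariate form is used, and possibly too few appendiceal deaths for more than description.

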4.4 Sample size calculation

Not applicable, given that the primary objective of this study is of descriptive nature.

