8. METHODS

A list of data items obtained from the SEER 17 database is provided in Table 1.

Table 1. Retrieved SEER Research Plus Data Items

Data item name	Category name
Patient ID	Other
Age recode with single ages and 85+	Race and Age (case data only) or Age at Diagnosis
Sex	Race, Sex, Year Dx, Registry, County
Race recode (White, Black, Other)	Race, Sex, Year Dx, Registry, County
Origin recode NHIA (Hispanic, Non-Hisp)	Race and Age (case data only) or Race, Sex, Year Dx, Registry, County
Race and origin recode (NHW, NHB, NHAIAN, NHAPI, Hispanic)	Race and Age (case data only) or Race, Sex, Year Dx, Registry, County
Year of diagnosis	Race, Sex, Year Dx, Registry, County
Sequence number	Multiple Primary Fields
Record number recode	Multiple Primary Fields
Total number of in situ/malignant tumors for patient	Multiple Primary Fields
Total number of benign/borderline tumors for patient	Multiple Primary Fields
First malignant primary indicator	Multiple Primary Fields
Primary by international rules	Multiple Primary Fields
Diagnostic Confirmation	Site and Morphology
Site recode ICD-O-3/WHO 2008	Site and Morphology
Site recode ICD-O-3/WHO 2008 (for SIRs)	Site and Morphology
Primary Site - labeled	Site and Morphology
Laterality	Site and Morphology
ICD-O-3 Hist/behav	Site and Morphology
Grade (thru 2017)	Site and Morphology
Grade Clinical (2018+)	Site and Morphology
Grade Pathological (2018+)	Site and Morphology
Site recode - rare tumors	Site and Morphology
ICCC site recode extended 3rd edition/IARC 2017	Site and Morphology
AYA site recode 2020 Revision	Site and Morphology
Lymphoid neoplasm recode 2021 Revision	Site and Morphology
SEER Brain and CNS Recode	Site and Morphology
TNM 7/CS v0204+ Schema (thru 2017)	Site and Morphology
CS Schema - AJCC 6th Edition	Site and Morphology
Schema ID (2018+)	Site and Morphology
AJCC ID (2018+)	Site and Morphology
EOD Schema ID Recode (2010+)	Site and Morphology
Combined Summary Stage (2004+)	Stage - Summary/Historic
Summary stage 2000 (1998-2017)	Stage - Summary/Historic
Derived EOD 2018 Stage Group (2018+)	Stage - 8th edition
Derived SEER Cmb Stg Grp (2016-2017)	Stage - 7th edition
Derived AJCC Stage Group, 7th ed (2010-2015)	Stage - 7th edition
Derived AJCC Stage Group, 6th ed (2004-2015)	Stage - 6th edition
SEER modified AJCC stage 3rd (1988-2003)	Stage - Other
Lymphoma - Ann Arbor Stage (1983-2015)	Stage - Other
Tumor Size Summary (2016+)	Extent of Disease
CS tumor size (2004-2015)	Extent of Disease

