EOD 10 - size (1988-2003)	Extent of Disease - Historic
Months from diagnosis to treatment	Therapy
RX Summ--Surg Prim Site (1998+)	Therapy
Reason no cancer-directed surgery	Therapy
Radiation recode	Therapy
Chemotherapy recode (yes, no/unk)	Therapy
B Symptoms Recode (2010+)	Site-Specific Data Items
CEA Pretreatment Interpretation Recode (2010+)	Site-Specific Data Items
Survival months	Cause of Death (COD) and Follow-up
Survival months flag	Cause of Death (COD) and Follow-up
Vital status recode (study cutoff used)	Cause of Death (COD) and Follow-up
COD to site recode	Cause of Death (COD) and Follow-up
SEER cause-specific death classification	Cause of Death (COD) and Follow-up
SEER other cause of death classification	Cause of Death (COD) and Follow-up

Patients are categorized into two age groups: children (aged 0-17 years at diagnosis) and young people aged 18-24 years at primary gastrointestinal cancer diagnosis. In principle, data is analyzed and presented by 1-year age category or by age group (<18 or 18-24 years at diagnosis), except for age distributions of specific patient populations (e.g. patients with colorectal carcinoma). When data from children and young people aged 18-24 years are analyzed together, then this is clearly stated in the accompanying text. Race is categorized into White, Black, and Other. Origin is categorized into Hispanic and non-Hispanic. Together, race and origin are reported in

Legend Table 2. Abbreviation: NOS, not otherwise specified. Symbols: * Contrary to the Rare Cancer Classification, cancers with ICD-O-3 morphology codes 8000-8009 ("neoplasms, NOS") and ICD-O-3 topography codes C015-C026 ("digestive organs") are not classified (e.g. morphology code 8002 as NEN; morphology codes 8000-8001 and 8003-8005 as epithelial tumors). Instead, these cancers are grouped within "rare other and unknown subtypes" in our study. This decision is made because – in our study population – the likelihood that digestive cancers of unspecified histologic subtype are of neuroendocrine or epithelial origin is not necessarily highest. In our young patient population, malignancies in these anatomic locations are relatively often other cancers, such as lymphomas, sarcomas or blastomas.

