Standardized incidence ratios (SIR) and 95% confidence intervals of second primary malignancies (SPM) in patients that survived i) two or more months, or ii) five or more years after initial gastrointestinal cancer diagnosis are estimated using the multiple primary (MP-SIR) session of SEER*Stat software. Analyses are performed by common gastrointestinal cancer subgroup (BL, UESL, NEN, HCC, HB, GC, and CRC). SIR calculations compare the observed second cancer incidence with the expected first primary cancer incidence in the age-, sex-, race- and calendar year-matched general population²⁹. The general population rates are available by cancer site, 5-year age categories, sex, race and 5-year diagnostic time periods.

A *P* value < 0.05 is considered statistically significant.

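### Table 4 gives non-Hispanic Other and unknown race a single hazard ratio, so that coefficient cannot be read cleanly as the prognosis of non-Hispanic Other patients

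*Combined protocol and SAP*

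**What the plan says.** Section 10.2 sets the purpose of the model as "To explore independent prognostic factors for overall survival of patients with common GI malignancies". It then specifies that "multivariable Cox regression analysis is performed with age at diagnosis, sex, race and origin, year of diagnosis, stage at diagnosis, and histologic category" (the last when relevant) are the included variables. Race and origin is thus a candidate prognostic factor with its own reported results, not only an adjustment term.

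Table 4 lays out the output for seven cancers. Its race-and-origin levels are non-Hispanic White (reference), non-Hispanic Black, "NH-Other/Unknown" and Hispanic. Its stage levels are localized, regional (reference), distant and, as a separate row, "Unknown/unstaged". Each row is to carry a number at risk, a hazard ratio with 95% CI and a P value. The section ends by stating that a P "value < 0.05 is considered statistically significant".

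Two places in section 8 describe the variable. The text says "Race is categorized into White, Black, and Other", with no unknown level. Table 1 lists the retrieved item "Race and origin recode (NHW, NHB, NHAIAN, NHAPI, Hispanic", which is finer than Table 4 and also names no unknown level. A sentence in section 8 on how race and origin are reported together breaks off in the available text, so a definition may have stood there.

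No expected counts are given. Section 4.4 on sample size reads "Not applicable, given that the primary objective of this study is of descriptive nature".

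**The concern.** A single coefficient is fitted to two kinds of patient: those known to belong to a non-Hispanic group other than White or Black, and those whose race is not known. The second is a state of the record, not a demographic group. The fitted hazard ratio is a weighted mixture of the two hazards, and a reader cannot tell from it what the prognosis of non-Hispanic Other patients is.

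The same model deals with missing stage by giving it a separate level, so missing covariate data are handled in two ways, and the legible text gives no reason. The retrieved recode allows the Other group to be defined by the two groups it names, so the pooling is not forced by the data.

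What is at stake is one line of the answer to secondary objective 2. If unknowns are few, that line is nearly right. If they are many and fare differently, a real association could be diluted, exaggerated or reversed, and the table would not show it.

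**Working it through.** The plan states no figure to reproduce: no event count, no number of unknown-race patients and no hazard for them. What can be done is a sensitivity calculation of the hazard ratio that a Cox model would return for the pooled row against non-Hispanic White.

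**Inputs.** From the documents: the pooled row and the reference group (Table 4). Everything else is assumed:
- true hazard ratio of non-Hispanic Other against White, h_O = 1.30 (also 1.00)
- hazard ratio of unknown race against White, h_U = 0.2, 0.5, 1.0 or 2.0
- unknown share of the pooled row, u = 2% to 30%
- exponential survival, with reference 5-year overall survival of 90% or 50%
- censoring uniform over 0-20 years, so G(t) = 1 − t/20
- a two-group comparison with 80% of patients in the reference group and no other covariates.

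**Formulas.** The reference hazard is λ = −ln(5-year OS)/5, which is −ln(0.90)/5 = 0.0211 or −ln(0.50)/5 = 0.1386 per year.

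- At risk, reference: R_W = 0.8·exp(−λt)·G
- At risk, pooled row: R_P = 0.2·[(1−u)·exp(−λ·h_O·t) + u·exp(−λ·h_U·t)]·G
- Deaths, reference: D_W = λ·R_W
- Deaths, pooled row: D_P = 0.2·λ·[(1−u)·h_O·exp(−λ·h_O·t) + u·h_U·exp(−λ·h_U·t)]·G

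The large-sample Cox estimate is exp(β), where β solves ∫{D_P − (D_P + D_W)·R_P·e^β/(R_P·e^β + R_W)}dt = 0.

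**Results for h_O = 1.30** (first figure: reference 5-year survival 90%; second: 50%)

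| u | h_U = 0.2 | h_U = 0.5 | h_U = 1.0 | h_U = 2.0 |
|---|---|---|---|---|
| 2% | 1.275 / 1.255 | 1.282 / 1.274 | 1.294 / 1.293 | 1.313 / 1.310 |
| 5% | 1.237 / 1.191 | 1.256 / 1.236 | 1.284 / 1.282 | 1.332 / 1.326 |
| 10% | 1.175 / 1.094 | 1.212 / 1.176 | 1.269 / 1.265 | 1.365 / 1.352 |
| 20% | 1.053 / 0.928 | 1.126 / 1.068 | 1.238 / 1.232 | 1.430 / 1.407 |
| 30% | 0.935 / 0.789 | 1.042 / 0.971 | 1.208 / 1.199 | 1.497 / 1.465 |

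**Hand check.** When deaths are few, the pooled value is close to (1−u)·h_O + u·h_U. For u = 10% and h_U = 0.5 this is 0.9 × 1.30 + 0.1 × 0.5 = 1.22, against 1.212 and 1.176 solved. The gap grows with mortality because higher-risk patients leave the risk set sooner.

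**Reading the table.** The largest shift at 2% is 1.30 − 1.255 = 0.045. At 20-30% the pooled value runs from 0.789 to 1.497. The direction depends on whether h_U lies below or above h_O. When h_O = h_U the row is homogeneous and the shift is zero; with both at 1.0 the solved value is 1.0 at every share.

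**The case against.** The case for leaving the row alone has several good parts.

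- **The plan pools elsewhere too.** For gastric and colorectal carcinoma, Table 3 puts other and unknown histology in one category, and Table 4 uses it. Stage is also an imperfect comparator, because it has no residual level that unknowns could join. This stands: the race row is not a lone departure from an otherwise uniform rule. It does not make the coefficient interpretable.
- **The label discloses the mixture.** True. A careful reader is warned, but cannot undo the mixture without the counts.
- **The row is narrower than all unknown race.** Hispanic has its own row, so by its label the pooled row holds only unknown-race patients not classed as Hispanic. This stands.
- **Sparse data.** There are seven cancers, and section 10.2 opens by stratifying results into two age groups. If that applies to Table 4, there are up to 7 × 2 = 14 fits, and an unknown level may be inestimable in some. This stands, and the fix must allow for it.
- **The missing text.** The broken-off sentence in section 8 may have explained the handling, so the absence of a definition is not held against the plan. Table 4 still pools.
- **Splitting is not a cure.** If race recording depends on outcome, the patients with recorded race are themselves selected, and a separate row does not recover an unbiased hazard ratio. This stands.

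A reader might go further and infer that the hazard ratio is in fact biased, that the bias runs downward because unknown-race patients are mostly long survivors, and that a disadvantage for Asian/Pacific Islander or American Indian/Alaska Native patients is being hidden. The documents support none of this. They say nothing about how completely race is recorded, what that depends on, or how these patients fare.

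**Conclusion.** The point holds as a matter of interpretability. The planned coefficient combines a demographic group with missing data, the retrieved data allow them to be separated, and the row should not be reported as the effect of being non-Hispanic Other.

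The actual shift cannot be computed from the documents. It needs both a material unknown share and a different hazard, and every magnitude above rests on assumed values for both. It would also be too strong to say that the row describes no real population: with very few unknowns it is in substance the Other group. That group is itself a composite of two groups that Table 1 names separately, so removing the unknowns would not make it homogeneous.

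The consequence is small in scope: one level of one covariate in an exploratory secondary analysis. The Kaplan-Meier survival estimates under the primary objective do not use this row. It is a worthwhile, low-cost improvement rather than a serious flaw.

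**What to change.** In Table 4 and section 8:

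- Define non-Hispanic Other as the Asian/Pacific Islander and American Indian/Alaska Native groups of the retrieved recode.
- Report the number of unknown-race patients for each cancer.
- Give unknown race its own row, as is done for stage.
- Where there are too few to estimate, exclude them from that model, state the number, and show the pooled version as a sensitivity analysis.

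If the counts turn out to be zero or negligible, the row label can simply be corrected and almost nothing else changes.

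The cost is one recode of a variable already retrieved, plus one extra coefficient or a few excluded cases per model. The confidence interval for non-Hispanic Other widens a little. If its width is driven by the deaths in that row, and unknowns contribute deaths in proportion to their share, the widening factor on the log scale is about 1/√(1−u): 1/√0.98 = 1.01 at 2%, 1/√0.90 = 1.05 at 10% and 1/√0.70 = 1.20 at 30%. The text should add that the split makes the row interpretable but does not remove bias if race recording itself depends on outcome. The same caution applies where unknown cases are excluded.
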